Engagement. Engagement is an ongoing process throughout therapy that should be actively monitored. This process is characterized by the therapist being empathically and authentically attuned to and connected to each individual on a personal level and being genuine in his/her interactions with the clients.

Assessment. At this stage, the therapist assesses the goals of both partners. The therapist also assesses what the focus of therapy will be and shares that plan with the participants.

End State:

At the end of session one and all of the rest of the sessions, both partners feel safe and accepted by the therapist, have some hope that the therapist will be able to help, and agree to return to therapy. In addition, the therapist has an initial idea about the major conflicts and interactional cycles, as well as the attachment positions of each individual.

Week 2: Assessment and Diagnosis

Goals:

The overall goal of assessment and diagnosis is to identify the negative interactional attachment cycles that occur and the feelings (overt and vulnerable) that everyone experiences during these cycles.

Interventions & Mechanisms:

Focusing on the interactional cycle. Focusing on the interactions is the key mechanism of this stage. Here the therapist aims to intervene the interactional cycle, that is, rigid patterns of negative interactions couples find difficult to change. To change these patterns, therapists utilize communication and expression of emotions to promote change in emotional, cognitive, and behavioral pathways. This is part of the process of making sure that the therapist has an understanding of the clients' experiences.

End State:

At the end of session two, the therapist has an initial idea about the major conflicts and interactional cycles as well as the attachment positions of each individual.

Principal Investigator: [name]

Protocol Summary for IRB: Feasibility Study of Couple Therapy Treatment for Situational Couple Violence (IRB# 09-13-27)

Week 3: Accessing Unacknowledged Emotions

Goals:

The goal of the third session is to identify the unacknowledged emotions (overt and vulnerable) that everyone experiences during interactional cycles.

Intervention & Mechanisms:

Tracking and reflecting the cycles. In this stage, the therapist tracks and reflects the cycles by identifying the process and structure of the interactions in terms of affect, attachment positions, and attachment behaviors (distance-withdrawer, pursuer), piecing them together from both partners' descriptions and direct observations, and then reflecting the process of these interactions back to the partners. While doing so, the therapist interrupts and redirects the conversation when any partner talks about things other than the interactional cycle of focus.

End State:

Both partners have an expanded view of the problem and acknowledge to a certain extent how their interactions contribute to the problem. Both partners feel safer, more comfortable, and more accepted by the therapist.

Week 4: Reframing Interactional Cycles

Goals:

The goal of reframing is to access the unacknowledged vulnerable feelings of both partners in therapy in the context of their defensive emotional experiences that hold their interactional cycle in place (distance-fear/pursuer-anger). Most people are usually unaware of these vulnerable emotions (fear, sadness, anger, shame) and do not explicitly express them in their interactions.

The purpose of reframing is to access and unearth these vulnerable feelings that are hidden by the overt and defensive, angry or stonewalling ones, making them an explicit part of the therapeutic dialogue.

Interventions & Mechanisms:

Vulnerable feelings are accessed by focusing on the actual emotional experiences of the partners that occur during the therapy sessions. The therapist actively invites all in the room to engage in and focus on these emotional experiences, then expands and reprocesses these experiences by using the following techniques.

Validation. Validation of each person's responses and emotions as legitimate and understandable is crucial during this stage of therapy. Validation helps the partners to stay in contact with their emotional experiences and removes one major block to their engagement with their emotional states – self-blame.

Heightening of emotions. Heightening of emotions is a way of helping individuals fully experience and resonate with their vulnerable emotions. The therapist highlights and intensifies key vulnerable emotions that arise in the session and are related to the attachment positions of each partner. This heightening of vulnerable feelings helps people to engage with their emotional experience more intensely and create a new way of interacting with their partner.

Principal Investigator: [name]

Protocol Summary for IRB: Feasibility Study of Couple Therapy Treatment for Situational Couple Violence (IRB# 09-13-27)

Heightening can be achieved by:

1. Maintaining a consistent and persistent focus on key vulnerable emotional responses. The therapist blocks exits or changes in the flow of experience that are likely to lessen the emotional intensity of the vulnerable feeling in that moment. This should not be confused with “venting” of emotion.
2. Repeating a phrase to heighten its impact, usually this is a catch phrase used by the person.
3. Using clear, poignant images or metaphors that crystallize experience, for example, heart sinking, the floor dropping out from under you, it burns you to see him do that. The therapist should use each person’s own language.
4. Directing individuals to enact their vulnerable emotional responses again.
5. Referring to bodily/physical reactions (e.g., I shake when I hear this. There is a catch in your voice as if it hurts to even put it in words.)

Evocative responding. This intervention focuses on the tentative, unclear, or emerging aspects of individuals’ experiences. The therapist may focus on the most poignant elements of an emotional/bodily response, the conflicting elements within that response, the action tendency inherent in the emotional experience, or how cues are perceived or processed by others in the room. The therapist may simply repeat certain phrases, offer an image or metaphor, or ask exploratory questions. These reflections and questions are offered tentatively, for the clients to accept, correct, or reject.

Emphatic stipulation. The therapist makes inferences about an individual’s current state and experience from nonverbal, interactional, and contextual cues, from the therapist’s empathic immersion in the client’s experience, and from knowledge of the interactional positions and patterns of the couple. Based on such inferences, the therapist offers a formulation of each partner’s experience that adds a new element, or puts elements together in a new way, thus helping everyone to crystallize his/her experience and process this experience one step further. Inferences are typically around defensive strategies and core catastrophic attachment fears. The goal of this mechanism is not to offer insight or labeling, but to facilitate more intense experiencing through the new understandings about emotions, thoughts, and behaviors that will arise.

End State

Each partner’s attachment longings emerge and begin to be clarified during reframing. The partners feel relief in being able to process and understand their own emotions and their relationship patterns; that is, they feel a sense of efficacy when they begin to realize that each person unwillingly has helped to create the relationship cycle (e.g., If I created it, maybe I can make it different). This is also the time when attachment wounds (past incidents that have damaged the attachment, and actively influence the way the relationship is defined in the present) are explored and clarified.

Week 5: Choreographing Change

Principal Investigator: [name]

Protocol Summary for IRB: Feasibility Study of Couple Therapy Treatment for Situational Couple Violence (IRB# 09-13-27)

Goals:

The therapist is involved in choreographing a series of change events in which individuals who typically withdraw from interaction are able to express their own emotional experiences and attachment desires, while staying engaged in the interactions. At the same time, the individuals who are typically critical or blaming are able to hear these expressions without shutting down their own vulnerable feelings and attachment desires. They, too, are able to remain fully engaged in the interactional cycles, expressing their own vulnerable feelings. In so doing, each partner is explicitly taking a new position with their partner and this new position elicits a reorganization of the interactional cycles.

Interventions & Mechanisms:

During the process of choreographing change, the therapist focuses on the attempts that individuals make to express their vulnerability directly to their partner and help them to do so. For example, when individuals are unable to express their own desires, the therapist helps them to identify these and encourages the direct expression of them to their partner. In addition, if individuals express what they want to the therapist, the therapist redirects them to share these feelings with the others in the room. At the same time, the therapist facilitates the listening and responding process of other individuals in the therapy room.

As more positive interactions emerge, the therapist tracks and reflects the changes to the original negative interactional cycles that have resulted in this more positive cycle. For example, as withdrawers experience their real fears of contact, process them, access more specific hurts, and directly express these to their partner, the therapist validates and reflects this new behavior. The partner may respond with some disbelief and detachment as they hear such a direct expression of the typically withdrawn members' feelings and what they will and won't do in the relationship. If this is the case, the therapist helps those withdrawers to stay focused on their own reactions and continue the dialogue with their partner.

At the same time, the therapist helps the partner who tends to be blaming to hear and deal with their anxiety about this new behavior from the withdrawer. The therapist helps the partner who has been critical and blaming in the past, to focus on themselves rather than on the withdrawer, accessing their own attachment fears and experiences, and processing them. The therapist helps the pursuer to access both their longing for connection and real fear of the dangers of connecting. The therapist helps this partner to share these experiences with the withdrawer.

Restructuring interactions. For both the withdrawing and critical partners, the therapist reframes their difficulties in stating desires or accepting new expressions as their own vulnerabilities and fears arising from past experience of negative cycles. The therapist choreographs enactments of present positions that are now more explicitly, consciously, and actively taken and shapes those interactions to include new elements from the newly synthesized experiences arising from engagement, thus turning new emotional experience into new interactions.

Principal Investigator: [name]

Protocol Summary for IRB: Feasibility Study of Couple Therapy Treatment for Situational Couple Violence (IRB# 09-13-27)

End State:

Each partner sees the other partner differently and interacts with them in a new way. Withdrawn partners are fully engaged in interactions, experiencing their own vulnerable feelings, and sharing them with their partner.

Week 6: Emotional Engagement

Goals:

In this stage, the therapist helps clients facilitate expression of needs and wants by restructuring interactions. The objective is to enable both partners state their own desires in the relationship context by staying engaged with their own emotional experience. By being open to their partner's emotional experiences, they will be able to state these desires in ways that increases the likelihood that these desires will be met by their partner. For example, instead of a wife demanding that her husband do something, she will be able to ask him. In turn, he will be able to respond honestly about whether or not he is able to comply at this time to this request. In this way, each person will be able to present his/her specific requests in a manner that pulls the other person toward him/her and maximizes the possibility that the others will be able to respond.

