The purpose of this study is to understand whether the couple therapy that is used in practice is effective in preventing situational couple violence. More specifically, we will focus on couples with mild to moderate forms of situational couple violence to investigate how couple therapy can be effective in preventing the escalation and recurrence of situational couple violence. For this purpose, the response of partners to therapy will be investigated by integrating self-report questionnaires and psycho-physiological markers of emotion. All couples who exhibit characteristics of characterological violence will be excluded from the study.

The change in partners' emotion regulation over the course of therapy will be measured using psycho-physiological markers of stress response. Using these measurements, the interplay between changes in violence and the emotion regulation of partners in relation to each other will be investigated in a dyadic (couple) context. More specifically, the following aims will be pursued to understand the relationship between couple therapy, emotion regulation, and violence:

Aim 1: Examine the associations between IPV and each partner's psychophysiological regulation in terms of Hypothalamic Pituitary Adrenal (HPA) activity and Parasympathetic Nervous System (PNS) activity. This aim will investigate whether dysregulation of HPA and PNS activity in each partner is correlated with the existence and intensity of IPV for the couple. Existence and intensity of IPV will be assessed using self and partner report questionnaires. HPA activity will be measured using salivary cortisol, and PNS activity will be measured using vagal tone and vagal regulation by using an eMotion Heart Rate Variability (HRV) sensor.

Aim 2: Examine the longitudinal effects of conjoint therapy on IPV and each partner's psychophysiological regulation in terms of HPA and PNS activity. This aim will investigate whether the reported intensity of IPV for couples decreases after couples start therapy and whether this change is correlated with regulation of HPA and PNS activity for each partner. This aim will examine the effect of couple therapy on each individual partner separately.

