Aim 3: Examine the longitudinal effects of partners' psychophysiological regulation on each other's psychophysiological regulation and on IPV. This aim will explore patterns of change in each partner's psychophysiological regulation as a function of their partner's psychophysiological regulation. More specifically, this aim will investigate whether couple therapy facilitates change by restructuring the relationship in such a way that the change in one partner's behavior helps the other partner regulate their emotions in a functional way.

Principal Investigator: [name]

Protocol Summary for IRB: Feasibility Study of Couple Therapy Treatment for Situational Couple Violence (IRB# 09-13-27)

Study Design

This study has a longitudinal design that requires therapy sessions over 8 weeks, with data collected at every visit. Couple therapy will be conducted using an attachment and affect regulation based therapy approach described below under “Couple Therapy”. Data will be collected in the form of self-report and partner-report measures, as well as physiological screening of the neuroendocrine system. These measures are described below under “Data Collection”. The flowchart for the design of the study is shown below.

After careful screening, eight couples will be enrolled in the study. The couples will be divided into two groups, each consisting of four couples. Distribution of participants to the two groups will be randomized. Group 1 will immediately begin 8 weeks of couple therapy and Group 2 will complete 8 weeks of couple therapy after an 8 week (+ or – 10 days) waiting period is completed.

The pre-test, post-test, and follow-up physiological data collection will be completed at the following times for couples beginning the 8 weeks of couple therapy:

- Baseline Pre-test: Before starting the therapy sessions.
- Post-test: One week (+ or – 5 days) after the end of the therapy session.
- Follow-up: Three months (+ or – 10 days) after the post-test.

The participants that are assigned to Group 2 will also complete the physiological data collection before starting the 8 week waiting period. When participating in the 8 week couple therapy Group, participants will complete a small number of assessments at each therapy session.

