The participants that are assigned to Group 2 will have one additional assessment session at baseline. In order to help those in Group 2 who will not be receiving therapy for the first 8 weeks, individuals in this group will be taught safety planning, given information on local resources to help victims of violence, and will be instructed in stress and anger management strategies. Following this 8 week waiting period, they will receive 8 weeks of couple therapy unless they choose not to. All the physiological and behavioral data collection will be repeated once Group 2 starts therapy.

If a couple discontinues after the baseline and before the end of the study (EOS), the EOS assessments should be obtained.

For couples in Group 1, involvement in the study will last throughout a period of five months with approximately 14 hours of active participation. For couples in Group 2, involvement in the study will last throughout a period of seven months with approximately 16 hours of active participation.

Couple Therapy

Each couple will receive couples therapy for 8 weekly sessions. Each therapy session will last approximately an hour. The therapy sessions will take place in UH Mood Disorders Program, room #12-126, on the 12th floor of the W.O. Walker Center. An attachment and affect regulation based therapy approach will be used in couple therapy.

Principal Investigator: [name]

Protocol Summary for IRB: Feasibility Study of Couple Therapy Treatment for Situational Couple Violence (IRB# 09-13-27)

The participants will receive standard couples therapy that they would have access to outside of the study. The therapy itself is not experimental, but rather it is the data collection, physical measures, and timing which are the experimental portions of the study.

All therapies will be conducted by the PI, [name]. [name] is a Licensed Marriage and Family Therapist and AAMFT (American Association of Marriage and Family Therapy) approved clinical supervisor.

Hypotheses

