- 5) Both partners must want couples therapy and both partners must desire to maintain the relationship.
- 6) Both individuals from the couple must participate concurrently, although they will sometimes be separated when asked questions of a sensitive nature.
- 7) Only heterosexual couples will be included in the study.
- 8) Both partners can be on psychotropic medication, if they are on medication and stable for past 12 month prior to enrollment, and no psychiatric hospitalization for past 2 years.

Exclusion Criteria:

- 1) Couples will be excluded from the study if there are indicators of severe intimate partner violence and/or characterological violence as this study targets couples with mild to moderate levels of violence. In order to distinguish between these two different types of violence, we will use specific items in the Conflict Tactic Scale (CTS) completed by both parties (Johnson, & Leone, 2005).

Severe and/or characterlogical violence in this study is defined as follows:

- If participants answer yes to both of the following items: "I punched or hit my partner with something that could hurt", "I kicked my partner".
- If participants answer yes to any of the following items: "I choked my partner," "I slammed my partner against a wall," "I beat up my partner" "I burned or scalded my partner on purpose," and "I used a knife or gun on my partner".
- One of the partners reports that a violent behavior was repeated at least six times in a year by their partner or themselves.

If one of the partners indicates that any of these behaviors was exhibited by their partner or by themselves, the couple will be excluded from the study. In other words, these behaviors will not be scored, the scale will be used to detect the existence of any of these behaviors and exclude the couple in the case any of these behaviors exist.

This conceptually based classification has been supported by factor analyses and by a growing recognition that the etiology and treatment of occasional minor violence (situational couple violence) may be quite different than the etiology of repeated severe assaults (characterlogical violence) (Gelles 1991; Hollzworth-Munroe and Stuart 1994; Johnson and Ferraro 2000; Straus and Gelles 1990).

- 2) Participants will also be excluded from the study if they answer yes to the following questions: "Do you have any firearm at home?", "In your previous relationships, did your partners ever tell you that you were physically abusive?"

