Table 2. Assessment schedule

Principal Investigator: [name]

Protocol Summary for IRB: Feasibility Study of Couple Therapy Treatment for Situational Couple Violence (IRB# 09-13-27)

Efficacy & Data Analysis

Data analysis plan

This study is designed to be an initial feasibility study to collect pilot data in pursuit of the following aims:

Aim 1: After the first wave of data collection (pretest), the cross sectional relations among the basic constructs of interest will be examined. These basic constructs are psychophysiological markers of emotion regulation and IPV. In order to understand how these markers are related to violence, t-tests will be used to understand this effect. Each partner's HPA and PNS activity is expected to be directly linked to the violence perpetrated by their partner.

Aim 2: The objective of this aim is to understand whether violence decreases over time following therapy and whether this decrease is accompanied by respective change in physiological markers of emotion regulation. For this purpose, series of chi-square-test will be used as well as qualitative analysis.

Aim 3: In order to represent the interaction between the emotion regulation of partners, links from emotion regulation of each partner to the emotion regulation of the other partner at the next time point are included. Qualitative analysis with a grounded theory approach will be used.

The proposed sample size (8 couples) is chosen as a tradeoff between data collection time and statistical power. Since this is a feasibility study, we chose to start with a small sample size. GPower was used to estimate statistical power for the primary hypotheses. Assuming 8 couples (16 participants), with 4 couples in each group and two waves of data each, the statistical significance can be detected. Specifically, with power = .40, this study can detect an effect size of $f = .80$ (Using t-test statistics). Also chi-square test will be used to test the effectiveness of the intervention with power = .40. With this level of power, this study can detect an effect size of $f = .60$ (Using chi-square statistics).

The PI will continually monitor the study design to determine if there is a need to make modifications or discontinue the study due to lack of efficacy from therapeutic intervention.

Safety

Compensation for research related injury

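### Only the contrast at about weeks 8–9 has a randomised no-therapy comparator; the 3-month follow-up is uncontrolled and should be labelled descriptive

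*Combined protocol and SAP*

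**What the plan says.** - **Purpose (Study Design & Objectives).** The study is to examine "how couple therapy can be effective in preventing the escalation and recurrence of situational couple violence".
- **Study Design, allocation.** The planned sample is eight couples, allocated as follows: "The couples will be divided into two groups, each consisting of four couples. Distribution of participants to the two groups will be randomized".
- **Study Design, comparator.** Group 1 starts therapy at once. "Group 2 will complete 8 weeks of couple therapy after an 8 week (+ or – 10 days) waiting period is completed". The section then adds: "Following this 8 week waiting period, they will receive 8 weeks of couple therapy unless they choose not to".
- **Study Design, assessments.** Pre-test comes before therapy. "Post-test: One week (+ or – 5 days) after the end of the therapy session". Follow-up is three months (plus or minus 10 days) after the post-test. Group 2's one additional assessment is at baseline, before the wait.
- **Data analysis plan, Aim 2.** The aim is to "understand whether violence decreases over time following therapy" and to see whether physiological markers change with it, using chi-square tests and qualitative analysis. No Group 1 versus Group 2 contrast is named, there is no definition of recurrence, and the role of the follow-up is not stated. The power paragraph counts two waves of data, while Study Design schedules pre-test, post-test and follow-up.
- **Risk Management, plans at the end of the protocol.** Couples who ask for more therapy after the eighth week may continue with the investigator.

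**The concern.** The stated purpose is causal: whether therapy prevents violence. The stated analysis of violence is a before-after reading within couples. Couples who enter because of recent violence, who are taught stress and anger management whichever group they are in, and who know they are being observed may report less violence later with or without couple therapy. Only a concurrent randomised group can separate these influences from the effect of therapy.

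The design supplies such a group, but only for about 8 weeks. Naming the 8-week contrast would not extend control to the follow-up, because the contrast ends before that period begins. No section says that the follow-up is uncontrolled. The effectiveness conclusion could therefore rest on before-after change or on a quiet follow-up, while the better comparison, already available from scheduled assessments, goes unspecified.

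**Working it through.** **Inputs (Study Design and Couple Therapy sections).** Therapy lasts 8 weeks. The wait is 8 weeks ± 10 days. The post-test is 1 week ± 5 days after therapy. Follow-up is three months ± 10 days after the post-test, taken here as 13 weeks. Stated involvement is five months for Group 1 and seven for Group 2. I use 4.345 weeks per month.

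**1. Reproduce the plan's own durations.**
- Group 1: 8 + 1 + 13 = 22 weeks; 22 / 4.345 = 5.1 months (stated: five).
- Group 2: 8 + 22 = 30 weeks; 30 / 4.345 = 6.9 months (stated: seven).

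Both agree, so the timeline is read correctly.

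**2. Place the groups on one calendar (weeks from the start of Group 1's therapy).**

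| Event | Nominal week | Range from the windows |
|---|---|---|
| Group 2 pre-therapy assessment and start of therapy | 8 | 6.6–9.4 (± 10 days) |
| Group 1 post-test | 9 | 8.3–9.7 (± 5 days) |
| Group 2 end of therapy | 16 | 14.6–17.4 (± 10 days) |
| Group 1 follow-up | 22 | 19.9–24.1 (± 15 days) |
| Group 2 follow-up | 30 | 26.4–33.6 (± 25 days) |

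At Group 1's follow-up, Group 2's scheduled therapy ended 22 − 16 = 6 weeks before. At the extremes of the windows the gap is 2.4 to 9.6 weeks, so it never closes. At Group 2's follow-up both groups have been offered therapy. Group 2 couples who decline therapy are at most four and self-selected, so they are not a randomised control.

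**3. Locate the randomised contrast.** The groups differ in couple therapy only up to about weeks 8–9. The 13 to 14 weeks that follow, up to Group 1's follow-up (22 − 9 = 13; 22 − 8 = 14), have no randomised comparator without couple therapy.

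**4. What a violence-free follow-up could show by itself.** The two-sided 95% exact lower limit when all n couples are violence-free is 0.025^(1/n): 39.8% for 4 of 4 and 63.1% for 8 of 8. The documents give no violence-free rate without therapy. Assuming 20% to 80% over three months, the chance that all four couples are violence-free with no effect of therapy is 0.2⁴ = 0.002 to 0.8⁴ = 0.41. For all eight it is below 0.001 to 0.8⁸ = 0.17. The reading depends on a rate that the design does not measure.

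**5. Illustration for a single behavior (assumption: Poisson, constant rate).** P(no event in 13 weeks) = exp(−rate × 13/52). For 1, 2, 3, 4 and 5 events a year this gives 78%, 61%, 47%, 37% and 29%. These are not couple-level rates. Four act-by-partner combinations at 2 a year each give exp(−8 × 0.25) = 13.5%; at 3 a year each, exp(−12 × 0.25) = 5%.

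**6. Strength of the randomised contrast.** With violence scored yes or no per couple and 4 couples against 4, complete separation gives a two-sided Fisher p of 2/70 = 0.029. If one couple falls out of place, p = 0.143. The contrast is protected from the biases of a before-after reading but is very imprecise.

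**The case against.** **Recurrence need not mean recurrence after therapy.** This stands. Couples enter already violent, so a new episode at any time after randomisation is a recurrence. The Data Collection section has violence questionnaires at every visit and uses the conflict scale throughout the study. A reader might infer that the study has no controlled information on recurrence at all. The documents do not support that: the weeks 8–9 contrast is a randomised look at recurrence in the first 8 weeks. What lacks a control is durability.

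**No misreading is planned.** This also stands. A reader might infer that the plan will count a quiet follow-up as prevention, but no section says so. The power paragraph's two groups and two waves even hint at a comparison at the end of the wait. Still, Aim 2 does not name that contrast, and its before-after wording permits the misreading.

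**The entry limit does not make a quiet follow-up likely.** Exclusion criterion 1 removes a couple if "One of the partners reports that a violent behavior was repeated at least six times in a year by their partner or themselves". One might infer that most couples would be event-free for three months without therapy. The limit is per behavior, and step 5 shows that a couple's total can be far higher.

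**The earlier treated series are not a yardstick.** One might set the 13-week figures beside the results in the literature section (65% violence-free; 43% recidivism). Those are 6-month results, and nothing says that those studies used this entry limit.

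**Losing the control is inherent in a wait-list design, and this is a feasibility study.** True, and this lowers the weight. It does not remove the effectiveness purpose or the need to say which comparison supports it.

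**Conclusion.** The point holds in a limited form. A randomised comparison of therapy with no couple therapy exists only at about weeks 8–9. The follow-up, at about week 22 for Group 1 and week 30 for Group 2, has no randomised comparator and may also reflect continued therapy. Neither low violence there nor before-after change alone can be credited to therapy.

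This rests on the scheduled timeline, which reproduces the stated five and seven months and survives the extremes of the visit windows. It does not rest on the Poisson or binomial illustrations, which use assumed rates. No couple therapy is not the same as no help: Group 2 receives safety planning, resource information and stress and anger management while waiting. The point is minor, given eight couples and a stated feasibility aim.

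**What to change.** In the Purpose section and in Aim 2 of the Data analysis plan:

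1. State that any conclusion about effectiveness, including on recurrence during the first 8 weeks, rests on the randomised Group 1 versus Group 2 contrast at about weeks 8–9: Group 1's post-test against Group 2's pre-therapy assessment. Say what period each report covers, since the two assessments are nominally a week apart, and report the estimate with its confidence interval. Make clear that Group 2's assessment precedes its first session; Study Design places the pre-test before therapy but also speaks of repeating data collection once therapy starts.
2. State that the 3-month follow-up is an uncontrolled, descriptive look at durability, that it may include further therapy, and that it is not evidence that therapy prevents later recurrence.

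If the single-behavior figures (29–78% event-free in 13 weeks at 1–5 a year) are cited, label them as an assumption for one behavior. I would not add a table of follow-up event rates beside the rate during Group 2's wait: no recall period for the scale is stated, and the wait yields only 4 × 8 = 32 couple-weeks.

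The cost is wording in two sections, with no new visits or couples and no change to the wait. The study gives up a causal claim about durability after therapy, but not about recurrence in the first 8 weeks.
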